#### **4.8.7 Conversion to Manual Procedure Data Collection**

The Investigator shall determine if it is necessary to convert to standard manual techniques to complete the endovascular robotic procedure. The Investigator should make this decision based on his/her medical assessment of the situation in accordance with the best interest of the subject. It is recommended that conversion to manual operation be performed at the discretion of the Investigator or if any of the following occur:

- The inability to navigate the guidewire(s), microcatheter(s), embolization coil(s) or stent-assist coiling using the CorPath GRX System as intended.
- Any clinical condition that requires rapid medical intervention. Details of manual technique to be documented are:
  - Planned or unplanned (e.g. physician preference, use of equipment not compatible with CorPath GRX);
  - If unplanned (e.g. embolization coils were undeliverable due to severe tortuosity), specify why.

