#### 3.2 Primary Effectiveness Endpoint

The primary effectiveness endpoint will be defined as successful completion of the robotic-assisted endovascular procedure absent any unplanned conversion to manual for guidewire or microcatheter navigation, embolization coil(s) or intracranial stent(s) deployment, or an inability to navigate vessel anatomy.

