#### **4.8.6 Specify Device to Be Used Robotically**

After arterial access prior to using the CorPath GRX System, the Investigator will specify which device he/she will plan to use robotically. If a device that is used robotically cannot be delivered to the target, cross the target or delivered into the target and conversion to manual is needed, it will be documented as an unplanned conversion to manual.

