4.2 Primary Effectiveness Endpoint

Objective: To assess effectiveness of using CorPath GRX for robotic-assisted endovascular procedure.

Hypothesis:

$H_0: p \leq 80\% \text{ (90\% - 10\% NI margin)}$

$H_a: p > 80\%,$

where p =proportion of patients with a successfully completed endovascular procedure.

Endpoint: The proportion of subjects with successful completion of the robotic-assisted endovascular procedure absent any unplanned conversion to manual for guidewire or microcatheter navigation, embolization coil(s) or intracranial stent(s) deployment, or an inability to navigate vessel anatomy.

Subjects to Include: Analysis Cohort

Statistical Analysis: The proportion of subjects with a successful procedure completion as defined will be summarized along with a 2-sided Clopper Pearson Exact 95% confidence interval. If the lower bound is greater than 80%, we will declare success and conclude that effectiveness is not inferior to the performance goal of 80%.

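### The primary effectiveness result depends on an operator-assigned planned/unplanned label for conversions to manual that neither document defines or ties to a time point

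*Protocol*

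**What the plan says.** Protocol 3.2 defines primary effectiveness as "successful completion of the robotic-assisted endovascular procedure absent any unplanned conversion to manual for guidewire or microcatheter navigation", and continues with coil and stent deployment and with inability to navigate. SAP 4.2 uses the same definition ("absent any unplanned conversion to manual for guidewire or microcatheter navigation, embolization coil(s) or intracranial stent(s) deployment").

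Three steps in the protocol bear on the label:

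- **Declaration.** Under 4.8.6, after arterial access and before robotic use, "the Investigator will specify which device he/she will plan to use robotically". Section 4.8.3 also lists the devices planned for robotic delivery among the data to collect.
- **Delivery failure.** Also in 4.8.6, if a device used robotically cannot reach, cross or enter the target and "conversion to manual is needed, it will be documented as an unplanned conversion to manual".
- **Recording.** Section 4.8.7 leaves the decision to the operator ("It is recommended that conversion to manual operation be performed at the discretion of the Investigator", or in listed circumstances). The nature of the conversion is documented as "Planned or unplanned (e.g. physician preference, use of equipment not compatible with CorPath GRX"). The next item reads "If unplanned (e.g. embolization coils were undeliverable due to severe tortuosity), specify why".

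Neither the definitions in protocol Section 13 nor the SAP says what makes a conversion planned.

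**The concern.** The word *unplanned* separates success from failure on the primary endpoint, and the person who applies it is the operator who made the switch, in an open single-arm trial judged against a fixed 80% goal. Suppose a device was declared robotic, the operator takes it over by hand during the case, and the reason given is preference. Section 4.8.6 does not clearly cover this, because no delivery failure is claimed. Section 4.8.7 names preference as an example without saying which label it belongs to. The case can be recorded as planned and scored as a success.

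No independent check of this label is named. Section 9.2 reviews clinical events, the Surveillance Committee (5.8) reviews complications and adverse events, and the core laboratory list (11.4) covers aneurysm location, occlusion grade and stenosis. Source verification confirms that the label was transcribed correctly, not that it was the right one.

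An error of this kind can only raise the success rate. With a pass mark set by a count, a handful of cases can decide the trial.

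**Working it through.** **Inputs.** n = 108, goal p0 = 80%, expected rate 90% (protocol 6.6, SAP 3.2). Success is declared if the lower limit of the two-sided 95% Clopper-Pearson interval exceeds 80% (SAP 4.2), which is a one-sided exact test at 0.025.

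**1. The plan's own figure.** The smallest r with P(X ≥ r | 108, 0.80) ≤ 0.025 is r = 95.

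- 95/108 = 88.0%, lower limit 80.3%: pass.
- 94/108 = 87.0%, lower limit 79.2%: no pass.
- P(X ≥ 95) = 2.1% at a true rate of 80% and 81.0% at 90%.

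The stated power of at least 80% with 108 subjects is reproduced. At most 13 failures are allowed (108 − 95).

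**2. Cases needed to change the result.**

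- 94 successes: relabelling 1 of the 14 failures gives 95, a pass.
- 92 successes (85.2%, lower limit 77.1%): relabelling 3 of the 16 failures gives 95, a pass.

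**3. Effect on the chance of a false pass.** Let e be the share of true failures that are open to relabelling (not delivery or navigation failures), and s the share of those recorded as planned. The documents give neither value. The apparent success rate at a true rate of 80% is

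p = 1 − 0.20 × (1 − e × s).

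With e = 0.25 (assumed):

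| s | e × s | p | P(X ≥ 95 of 108) |
|---|---|---|---|
| 0 | 0 | 0.8000 | 2.1% |
| 10% | 0.025 | 0.8050 | 2.8% |
| 25% | 0.0625 | 0.8125 | 4.3% |
| 50% | 0.125 | 0.8250 | 8.1% |
| 100% | 0.25 | 0.8500 | 23.8% |

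With e = 0.10 (assumed), s = 10%, 25% and 50% give 2.4%, 2.8% and 3.7%.

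**4. Cost of stricter scoring.** The pass mark and the 2.1% error rate do not change. If counting these switches lowers the true success rate from 90% to 89%, exact power falls from 81.0% to 70.1%.

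**The case against.** The strongest reply is that the protocol already contains most of what is needed. Planned devices go to the Eligibility Committee in advance (4.6.3) and those for robotic use are specified before the robotic part begins, so in ordinary usage *planned* means what that record shows. Delivery failures must be recorded as unplanned, and inability to navigate fails the endpoint whatever the label. A relabelled delivery failure would also appear in the device-level secondary endpoints taken from CRF 9 (SAP 4.4.2 to 4.4.4 and 4.4.12). All of this stands, and it is why the gap is narrow. It does not close the gap, because no sentence makes the declaration the test of *planned*.

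Three stronger readings are tempting, and the documents do not support them.

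- A reader might infer that 4.8.7 assigns preference and incompatible equipment to *planned*, and that these reasons arise during the case. The separate example for *unplanned* makes the first part natural, but grammatically the examples follow both words, and incompatible equipment may be known beforehand. The form itself is not in the documents.
- A reader might infer that 4.8.6 makes a conversion unplanned only when delivery fails. It states one sufficient condition and does not classify the remaining switches as planned.
- A reader might apply relabelling to all failures, which gives an 81.0% chance of passing at a true rate of 80% if half are relabelled (p = 0.90). Delivery failures and inability to navigate are already failures under the text, so that is the wrong base.

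**Conclusion.** The concern holds in a limited form. The scoring of a switch to manual for a non-delivery reason is left to an undefined label applied by the operator, and following the text as written can turn such switches into primary successes. Once the data are in, an analyst has no rule by which to correct this.

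The size depends on how many failures are of this kind, which the documents do not say. If they are a quarter of failures, the chance of passing at a true rate of 80% rises from 2.1% to between 2.8% and 8.1% when 10% to 50% of them are relabelled, and to 23.8% if all are. If they are a tenth, it stays at or below 3.7% when up to half are relabelled. The sensitivity to single cases needs no such assumption: one relabelled case changes 94/108 into a pass.

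The documents do not show that any operator would misuse the label, and the stated sample size and power are correct. This is a cheap improvement to the definition of the primary endpoint.

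**What to change.** In protocol 4.8.6 and 4.8.7 and in SAP 4.2, add a rule for endpoint scoring:

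- A conversion is *planned* only if that manual step was recorded in the 4.8.6 declaration before the robotic start.
- Every other switch to manual navigation or deployment of a device declared robotic is *unplanned* and counts as a failure, whatever the reason given.
- The routine manual loading, removal and exchange steps of the 4.8.5 workflow (for example loading the stent, removing the guidewire from the cassette, exchanging coils) are not conversions. Without this exclusion, a rule covering any manual handling would fail ordinary cases.

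Apply the rule in the analysis by comparing each subject's pre-robotic declaration with the CRF 9 record. CRF 9 is not in the documents, so confirm that it shows manual takeover for each device.

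The cost is wording in the two documents and possibly in the form. The observed success rate may be lower, and power is sensitive to this (81.0% at a true rate of 90%, 70.1% at 89%). The rule concerns scoring only and leaves the investigator's freedom to convert unchanged.

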#### **4.8.8 Device Malfunction Data Collection**

All CorPath GRX System device malfunctions will be documented in the EDC. If the device malfunction is related to a Device-Related Adverse Event (AE), the AE will be entered into the EDC and each site will follow their internal policies for AE reporting.

#### 4.8.9 Post-CorPath Data Collection

##### Post-CorPath Procedure Medication Regimen

Follow standard operator and institutional routines for recommended anticoagulation and anti-platelet regimens.

##### Post-CorPath Procedure Subject Evaluations

- NIH Stroke Scale (NIHSS) and Modified Rankin Scale (mRS) conducted by a trained person with appropriate qualifications to perform these evaluations are required to be performed within 24-hours post procedure or prior to discharge, whichever occurs first.
- Raymond Grade-Roy Occlusion Classification Scale conducted by a trained person with appropriate qualifications to perform this evaluation:
  - Class (I): Complete occlusion – complete obliteration of the aneurysm
  - Class (II): Residual neck – persistence of any portion of the original defect of the arterial wall as seen on any single projection, but without opacification of the aneurysmal sac.
  - Class (III): Residual aneurysm – opacification of the aneurysmal sac.
    - Class IIIa: contrast opacification within the coil mesh
    - Class IIIb: contrast opacification outside coil mesh
- Additional post procedure clinical assessment (scales/scores) is left to the discretion of the investigator and shall be dictated by the patient's clinical symptoms
- Record of all Adverse Events (AEs)
- If clinically indicated by the Investigator and/or if performed under standard hospital procedure, record lab values closest to 24-hours post-procedure or discharge:
  - Hemoglobin (HGB)
  - Hematocrit (HCT)
  - Activated Partial Thromboplastin Time (aPTT)
  - Platelet count
  - International Normalized Ratio (INR)
  - Serum Creatinine
  - Glomerular Filtration Rate (GFR)

- Before the subject is discharged from the hospital, it is recommended that telephone numbers and contact information be confirmed with the subject (and/or authorized legal guardian) to ensure the ability to contact him/her after discharge from the hospital for scheduling of the 90-day ( $\pm$  14 days) telephone evaluation.

#### 4.8.10 Follow-Up Evaluations

The following assessments will be completed at the specified time points below.

- 90-Day Follow-Up ( $\pm$  14 days) via a telephone evaluation**
  - Functional outcomes assessment to include Modified Rankin Scale (mRS)
  - Record any adverse events or additional interventions since time of hospital discharge
- 180-Day Follow-Up ( $\pm$  30 days)**
  - Digital Subtraction Angiography (DSA), Computed Tomography Angiography (CTA), or Magnetic Resonance Angiography (MRA) / Magnetic Resonance Imaging (MRI) of the brain/head
  - Functional outcomes assessment to include Modified Rankin Scale (mRS)
  - Raymond-Roy Occlusion Classification
  - Record any adverse events or additional interventions since time of hospital discharge.

#### 4.8.11 Schedule of Data Collection

Data collected for all subjects enrolled in this study should include the tests and procedures listed in the following Schedule of Activities (Table 1), many of which are part of routine data collection for all endovascular robotic procedures.

**Table 1: Schedule of Activities**

	Pre-Procedure	Procedure	Post-Procedure	90-day BY PHONE	180-day	Un-Scheduled Visit
		Day (0)	(24-hours post-procedure or hosp. discharge)	±14-days	±30-days	
Patient Eligibility Criteria	X					
Submit to Eligibility Committee						

 
• Clinical history
 
• Unruptured Intracranial Aneurysm Treatment Score
 
• Treatment plan
 
• ≥ 4 angiographic (DSA or CTA/MRA) images
 
	X					
Medical History	X 					
Digital Subtraction Angiography (DSA), Computed Tomography Angiography (CTA), or Magnetic Resonance Angiography (MRA)/Magnetic Resonance Imaging (MRI) of the brain/head	X 				X 	
Clinical assessment & Physical exam including:						

 
• Modified Rankin Scale (mRS)
 
• National Institutes of Health Stroke Scale (NIHSS) scale
 
	X		X	X 	X 	X 
Raymond Grade-Roy Occlusion Classification Scale	X 	X			X	
Laboratory Tests: hemoglobin, hematocrit, activated partial thromboplastin time, platelet count, international normalized ratio, pregnancy test, serum creatinine and glomerular filtration rate.	X 		X 			
Procedure Parameters		X				
Catheter Angiography		X 				
Contrast volume		X				
Record of AEs		X	X	X	X	X
Data for aneurysm assessment e.g. tortuosity, proximal & distal vessel diameter, target aneurysm measurements.		X			X	

 Within 7 days of index procedure.

 If performed under standard hospital procedure.

 For previously coiled aneurysms.

 Female subjects of child-bearing potential must have negative pregnancy test (urine or serum).

 Includes angiograms in the anterior posterior, lateral and working positions for analysis by a core laboratory.

 Telephone assessment and mRS is required. Other post procedure clinical assessment (scales/scores/grades) is left to the discretion of the investigator and shall be dictated by the patient's clinical symptoms.

 Post scans will be sent to the core laboratory for analysis.

 mRS is required. Other post procedure clinical assessment (scales/scores/grades) is left to the discretion of the investigator and shall be dictated by the patient's clinical symptoms.

 If visit is related to target aneurysm or potentially associated AE/SAE

## 5. ADVERSE EVENTS AND COMPLICATIONS

Throughout the course of the clinical investigation, all adverse events will be recorded on the applicable **ADVERSE EVENT** CRF and in the subject's medical records. In this study, adverse events will be defined and classified per ISO 14155:2020(E) Clinical Investigations of Medical Devices in Human Subjects - Good Clinical Practice, and as further described in this protocol. The date of onset, date of resolution, severity, and action taken will be evaluated by the Investigator. The relationship to the device, relationship to the procedure, and clinical significance will be evaluated. The neurological outcomes and adverse events will be reported.

### 5.1 Adverse Event Classification and Definitions

An Adverse Event (AE) is any untoward medical occurrence, unintended disease or injury, or untoward clinical signs (including abnormal laboratory findings) in subjects, users or other persons, whether or not related to the medical device (ISO 14155:2011).

NOTE 1: This definition includes events related to the medical device or the comparator.

NOTE 2: This definition includes events related to the procedures involved.

NOTE 3: For users or other persons, this definition is restricted to events related to medical devices.

Disease signs and symptoms that existed prior to study participation are not considered AEs unless the condition recurs after the subject has recovered from pre-existing condition, or the condition worsens in intensity or frequency during the study.

A Serious Adverse Event (SAE), as per the European Standard ISO 14155:2020(E), is an AE that led to any of the following:

- a) Death
- b). Serious deterioration in the health of subject, users or other persons as defined by one or more of the following:
  - 1) a life-threatening illness or injury, or
  - 2) a permanent impairment of a body structure or body function including chronic diseases, or

- 3) in-patient or prolonged hospitalization, or
- 4) medical or surgical intervention to prevent life-threatening illness or injury, or permanent impairment to a body structure or body function,
- c) Foetal distress, foetal death, a congenital abnormality or birth defect including physical or mental impairment.

Planned hospitalization for a pre-existing condition, or a procedure required by the protocol, without serious deterioration in health, is not considered a serious adverse event.

In the current study indication, examples of a Serious Adverse Event (SAE) are:

- Incidence of death 24-hours post procedure
- Target aneurysm rupture
- Vessel perforation
- Vessel dissection
- Thromboembolic complication
- Failure to navigate to target
- Device failure to respond to input, or other intra-operative device failure

## 5.2 Adverse Event Assessments

### Relatedness:

- Procedure-related: Event has a strong temporal relationship to the study procedure. This includes AEs attributable to any device(s) used at procedure, such as access devices, delivery microcatheters, embolic coils, non-ionic contrast, guidewires, or any other adjunctive, approved/cleared device for treatment of intracranial aneurysms.
- Device-related: Event has a strong temporal relationship to the CorPath GRX System.
- Unknown: Event relationship cannot be attributed to any of the above categories and remains undetermined.

### 5.3 Procedure-Related Adverse Event

An adverse event is procedure-related when, in the judgment of the Investigator; it is reasonable to believe that the event occurs from the endovascular robotic procedure, irrespective of the device.

### 5.4 Device-Related Adverse Event

An adverse event is device-related when, in the judgment of the Investigator, the clinical event has a reasonable time sequence associated with use of the CorPath GRX System and is unlikely to be attributed to concurrent disease or other procedures or medications. It is reasonable to believe that the CorPath GRX System directly caused or contributed to the adverse event.

### 5.5 Event Reporting Requirements

Any adverse event that occurs during the course of the study must be recorded and reported using the appropriate **Adverse Event** eCRF and also recorded in the subject's medical records. These will include events occurring from the point of consent until a subject exits the study. The Investigator must sign each AE eCRF report. Investigators must obtain all information available to determine the causality and outcome of the AE and to assess whether it meets the criteria for classification as serious and the relationship of each adverse event to the procedure or device. This determines whether it requires notification to the Sponsor, regulatory agency, and as applicable, EC, within the specified reporting timeframe. AEs will be categorized using the definitions in Section 5.1 – 5.4.

Pre-existing medical conditions or symptoms occurring prior to the start of the procedure should not be reported as adverse events. In the situation where there is a worsening of a pre-existing medical condition or symptom due to a study related procedure, an adverse event should be reported.

In the case of any **AE**, the Investigator shall submit to Corindus a report within 10 working days after the Investigator first learns of the event.

The Investigator is required to report all SAEs within 24-hours after first learning of the event to  
Version Date: May 21, 2021

*This confidential document is the property of Corindus, Inc. and shall not be reproduced, distributed, disclosed or used without the express written consent of Corindus, Inc.*

the Sponsor. The primary method of reporting SAEs will be through the eCRFs. If the database is unavailable, the investigator may fax or email in the information. As soon as the database becomes available, the investigator must complete data entry. Depending upon the nature and seriousness of the adverse event, the Sponsor may request the Investigator to provide anonymous copies of the subject's available supporting documentation (such as the subject's laboratory tests, hospital records, discharge reports, autopsy reports, Investigator summaries, etc.) to document the adverse event. The Sponsor is responsible in Europe for ensuring that the required and adequate information concerning the reported SAE is relayed to the appropriate Ethics Committee and Competent Authority using the MEDDEV 2.7/3 SAE Report Table. All other adverse events (i.e. other than serious adverse events) must be recorded on the appropriate adverse event eCRF.

Corindus, in cooperation with the Investigator, will assess all serious adverse events for potentially reporting to the Regulatory Authorities and EC.

For any adverse event that is ongoing at the time of the initial report, periodic follow-up information is required until the adverse event is resolved or is judged to be chronically stable, or until the conclusion of the study for the subject. The site should submit relevant follow-up information related to the adverse event as soon as it is available.

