### 1.2 Background

Subarachnoid hemorrhage is a life-threatening form of stroke with an estimated fatality rate between 26 and 36%. In approximately 80% of cases, subarachnoid hemorrhage is caused by the rupture of an intracranial saccular aneurysm. Aneurysms occur when structural abnormalities in the walls of the cerebral arteries cause weakening, thinning, and out-pouching of the vessel wall. They are frequently located at bifurcations within the proximal circle of Willis and approximately 20-50% of such aneurysms eventually rupture. While the incidence of subarachnoid hemorrhage varies widely from country to country and may be as high as 15 to 20 per 100,000 in Finland and Japan, its overall worldwide incidence is estimated to be 9.1 per 100,000 persons. As many as 30,000 Americans are affected per year.

Patients who survive subarachnoid hemorrhage long enough to be stabilized medically may experience cerebral vasospasm, delayed cerebral ischemia, hydrocephalus, deep venous thrombosis, and numerous medical sequelae, along with long-lasting neuropsychological changes, loss of productive years, and diminished quality of life. They are also at serious risk of re-rupture, and therefore it is usually appropriate for them to undergo treatment to minimize aneurysmal recurrence or re-rupture.

Meanwhile, it has been estimated that the remaining 50% to 80% of intracranial aneurysms present in the general population never rupture. The prevalence of unruptured intracranial aneurysms (UIA) in the general adult population has been estimated at between 1% and 5%, based on autopsy studies. Many are asymptomatic and detected only as incidental findings during cerebral imaging for other conditions. Others may cause headaches, seizures, cranial nerve palsies, focal neurologic deficits, and distal embolic ischemic events.

Due to the severe consequences of aneurysmal rupture, once a UIA is detected, a decision must be made between managing the patient conservatively or treating the aneurysm to prevent future rupture. While current clinical evidence favors treatment for ruptured aneurysms, the

decision to intervene for UIA is less straightforward and must balance the risk-benefit profile of the available interventions against the risks and benefits of watchful waiting.

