#### 3.4 Secondary Endpoints

Several secondary endpoints will be examined in this trial, including the following:

- 1. Clinical Outcome** - Clinical outcome as measured by Modified Rankin Scale. This is assessed at 90-Day Follow-Up ( $\pm 14$  days) and 180-Day Follow-Up ( $\pm 30$  days from the procedure date);
- 2. Robotically Navigate Device to the Target Aneurysm** - Defined as successful advancement of devices to the target aneurysm robotically;
- 3. Robotically Navigate Device *into* the Target Aneurysm** - Defined as successful navigation of device into the target aneurysm robotically;
- 4. Robotically Deploy Therapeutic Device *into* Target Aneurysm** - Defined as successful deployment of therapeutic device into the target aneurysm robotically;
- 5. Overall Procedure Time** - Defined as the time measured from the insertion of the access sheath/catheter until the removal of the microcatheter;

6. **Robotic Procedure Time** - Defined as the time measured from the first device used robotically until the removal of the microcatheter;
7. **Fluoroscopy Time** - Total fluoroscopy utilized during the procedure as recorded by the Imaging System;
8. **Patient Radiation Exposure** - DAP (dose-area-product) and CD/AK (cumulative dose/air kerma) as recorded during the procedure;
9. **Contrast Volume** - Total contrast used during the procedure;
10. **Adverse Events** - All adverse events (AEs) from the start of the CorPath GRX procedure until the end of the study will be summarized.
11. **Thromboembolic Events** - Defined as rate of thromboembolic events occurring up to 180-days following the robotic-assisted procedure;
12. **Devices Used Robotically** - All devices used will be recorded as successful or unsuccessful in conjunction with the CorPath GRX System;
13. **Aneurysm Occlusion** - Angiographic assessment of aneurysm occlusion grade according to the Raymond-Roy classification scale, parent-vessel compromise, and occlusion durability as assessed from an independent core laboratory. This will be assessed post-procedure and at a 180-day follow-up.

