## 5.8 Surveillance Committee

A Surveillance Committee will be composed of three expert physicians in the field of interventional neuroradiology and/or neurosurgery, who are independent and not directly involved in the conduct of the trial. The purpose of the committee is to review and adjudicate all complications/adverse events as they occur over the course of the study (classify, identify causal relationship between event and device, procedure or subject). The committee will also review and adjudicate, as necessary, issues relating to classification of events as major (serious) or minor (non-serious), and attribution to system, treatment and/or disease. The neurological outcomes and adverse events will be reported under the clinical investigation and any imaging generated will be forwarded to the committee. The committee will analyze the relationship between the images and the cause of the neurological deterioration. Any overall trends or conclusions drawn from these analyses will be reported; however, no specific criteria will be applied.

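### Protocol 5.5 ties the reporting of a worsened pre-existing condition to procedural cause, at odds with 5.1 and with its own opening rule, so site causality judgments may filter adverse events

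*Protocol*

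**What the plan says.** Protocol 5.1 defines an adverse event without regard to relatedness to the device. It excludes signs and symptoms that existed before the study, unless the condition recurs after recovery, "or the condition worsens in intensity or frequency during the study". It attaches no causal condition to that worsening.

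Protocol 5.5 opens by requiring that any adverse event during the study be recorded and reported, from consent until study exit, and it refers to the definitions in 5.1 to 5.4. Its next paragraph deals with pre-existing conditions: "Pre-existing medical conditions or symptoms occurring prior to the start of the procedure should not be reported as adverse events". The only exception stated there is for "worsening of a pre-existing medical condition or symptom due to a study related procedure, an adverse event should be reported".

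Protocol 5.8 sets up an independent Surveillance Committee to review and adjudicate all adverse events ("classify, identify causal relationship between event and device, procedure or subject"). Secondary endpoint 10 in Protocol 3.4 states: "All adverse events (AEs) from the start of the CorPath GRX procedure until the end of the study will be summarized". SAP 4.4.10 breaks the summary down by term, seriousness, and relatedness to device and procedure.

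**The concern.** Relatedness should be an attribute of a reported event. The specific sentence in 5.5 makes it a condition for reporting. The person applying the condition is the investigator, who operates the system (Protocol 4.8.5) and judges procedure-relatedness (5.3). The committee meant to make that judgment independently can be left without the events that the site has attributed to the patient or the underlying disease.

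The symptoms concerned matter in this trial. Of unruptured aneurysms that are not silent, the Background section says: "Others may cause headaches, seizures, cranial nerve palsies, focal neurologic deficits, and distal embolic ischemic events". Headache, seizure, neurological deficit and visual impairment are also on the list of anticipated adverse events in 5.6. The same symptom can therefore be a baseline condition in one patient and a complication in another. No eligibility criterion in 4.6 limits baseline mRS or NIHSS, and previously coiled aneurysms are foreseen in 4.8.2. At stake is whether the all-adverse-event summary is complete.

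**Working it through.** No arithmetic applies, so the check sets the provisions side by side.

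| Situation | Protocol 5.1 | 5.5, opening rule | 5.5, paragraph on pre-existing conditions |
|---|---|---|---|
| Pre-existing condition, unchanged | Not an adverse event | Not reported | Not reported |
| Pre-existing condition worsens, attributed to a study procedure | Adverse event | Reported | Reported |
| Pre-existing condition worsens, attributed to another cause | Adverse event | Reported | No instruction to report; the stated default is not to report |
| New event | Adverse event | Reported | Not addressed |

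The provisions diverge only in the third row. Section 5.5 conflicts there both with 5.1 and with its own first sentence.

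**Can the divergence reach the data?**

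1. *Who decides.* Procedure-relatedness is a matter of investigator judgment (5.3), so the site decides whether a case falls in row two or row three.
2. *What the committee receives.* Its remit is all adverse events (5.8), but endpoint adjudication under 9.2 works from narratives and source data supplied by sites. Section 5.8 also sends it any imaging generated, which is a partial second route.
3. *Whether monitoring would catch it.* Section 8.2 provides 100% source document verification. A monitor applying the specific sentence in 5.5 would have no reason to query a worsening that the site judged unrelated.
4. *Whether another measurement would show it.* NIHSS and mRS are required in every subject within 24 hours or before discharge (4.8.9), whatever the cause of a change. At 90 and 180 days the protocol requires mRS and leaves other scales to the investigator (Table 1, notes 6 and 8). SAP 4.4.1 refers to an NIHSS score on the 180-day form, but the protocol does not make it mandatory. Neurological worsening after discharge that does not move the mRS therefore depends largely on adverse event reporting.

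**Which endpoints are touched?** Secondary endpoint 10 is touched directly. The components of the primary safety endpoint (rupture, other vessel injury, and thromboembolic events with an NIHSS change of at least 4) are normally new events and fall in row four. The plausible route to the primary endpoint is an early neurological decline that the site ascribes to a pre-existing deficit, and the mandatory post-procedure NIHSS guards against that.

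**Can the loss be sized?** The expected number of subjects affected would be the number treated × the share with a relevant pre-existing condition × the share who worsen × the share judged unrelated and left unreported. The documents give the first factor (108 planned) and none of the others.

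**The case against.** The strongest reply is that nothing in 5.5 forbids reporting other worsening. The opening sentence requires any adverse event to be reported and points to the definitions, under which worsening qualifies. The introduction to section 5 and the follow-up instructions in 4.8.10 also call for adverse events to be recorded without a causal test. The sentence barring pre-existing conditions can be read as meaning the baseline state alone. In addition, 5.2 describes procedure-related events by a strong temporal relationship, which most worsening close to the procedure would meet.

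Much of this stands. It makes the problem an internal inconsistency that sites may resolve differently, and it moves the likely effect towards late worsening. It does not remove the problem: a coordinator with a question about a pre-existing condition will turn to the sentences written for that case, and those name a single, causal exception.

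A reader might infer three stronger things that the documents do not support:

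- *The committee never sees such worsening.* Sites following the opening sentence will report it, and imaging reaches the committee separately.
- *The unrelated-worsening row of the adverse event table will be empty by design.* SAP 4.4.10 plans no breakdown by pre-existing status, and the categories in 5.2 are procedure-related, device-related and unknown, with no category for unrelated.
- *The primary safety conclusion is at risk.* With 108 subjects the goal is met with at most 8 events (exact upper bound 14.07%) and missed with 9 (15.23%), so one lost primary event could matter at that boundary. But primary events are normally new ones, to which the sentence does not apply, and NIHSS is mandatory after the procedure.

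**Conclusion.** The inconsistency is real and worth correcting. Sites that follow the specific sentence in 5.5 may omit worsening that 5.1 defines as an adverse event, which lets the investigator's causality judgment filter what reaches the Surveillance Committee. The effect is mainly on secondary endpoint 10, a descriptive summary without a hypothesis test, and within it on neurological worsening after discharge. The primary safety endpoint is little exposed. No count of lost events can be supported from the documents.

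The conclusion rests on one assumption about conduct: that at least some sites will follow the specific sentence in preference to the general one.

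**What to change.** In 5.5, delete the words that make a study procedure the required cause, and align the sentence with 5.1. For example: *Worsening of a pre-existing condition or symptom, in intensity or frequency, at any time during the study is reported as an adverse event whatever its cause; the investigator records an opinion on relatedness and the Surveillance Committee adjudicates it.*

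The window should be the study, not the period after the start of the procedure. Section 5.1 uses the study, and 5.5 collects events from consent, so a later start would leave a new gap between consent and procedure. Endpoint 10 can still summarize events from the start of the procedure.

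The cost is one sentence in the next amendment, a short memo to sites and a few more adverse event forms.
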